## 5.0 Study Design and Statistical Analysis Plan

*5.1 Describe the basic study design/approach*

Simple randomized controlled trial comparing two groups in reducing post-operative pain from scleral buckle surgery -

1. Peribulbar irrigation of triamcinolone acetonide (Experimental Group)
2. Balanced Salt Solution (Control Group)

*5.2 Describe corresponding data analysis plan/approach*

Parametric analysis of experimental and control groups using students' t-test for primary endpoint, secondary endpoint of pain and analgesic consumption will be analyzed similarly. Secondary endpoints of nausea and vomiting score will be analyzed via non-parametric analysis (Mann-Whitney U test)

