## 4.0 Study Endpoints

### 4.1 *Describe the primary and secondary study endpoints*

Primary Endpoint:

- Statistically significant reduction in pain as measured by 11-point Numerical Rating Scale at 1-day post-op. We are powered to detect a reduction in 2 points on the NRS scale.

Secondary Endpoints:

- Statistically significant reduction in pain as measured by 11-point Numerical Rating Scale at 1-2 weeks post-op.
- Statistically significant reduction in pain as measured by 11-point Verbal Rating Scale at 6 months post-op.
- Significant reduction in analgesics consumed post-operatively (self-reported pill count) at 1-day post op
- Significant reduction in analgesics consumed post-operatively (self-reported pill count) at 1-2 weeks post op
- Significant reduction in Nausea and Vomiting Score at 1 day post-op.
- Significant reduction in Nausea and Vomiting Score at 1-2 weeks post-op.

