## 8.0 Procedures Involved

8.1 *Describe and explain the study design.*

Randomized Control Trial. Subjects will be patients at Vistar Eye Center who are undergoing scleral buckle surgery for rhegmatogenous retinal detachment. Patients of this indication will be consented and enrolled in the trial as detailed in section 24, and randomized (by coin-flip) into one of two arms, the control or the experimental. Patients in both arms of the study will be screened for IOP via handheld digital tonometry (tonopen) and will undergo standard scleral buckle procedures, including irrigation with 1 ml .75% Marcaine for local anesthesia (as is standard for all surgeries). At time of surgery, patients in the experimental group will receive irrigation of 1 ml (40 mg/mL) triamcinolone around the bed of applied scleral buckle distributed equally in all 4 quadrants (.25 ml per quadrant) under the tenon layer of the eye. Patients in the control group will be given irrigation around the applied scleral buckle of 1 ml balanced salt solution instead of triamcinolone. Patients will be masked to the treatment group assignment. The surgeon cannot be masked, as the triamcinolone solution is white and the balanced salt solution is clear. Intraoperative details will be recorded in the EMR about the surgery in both groups, including duration of surgery, time of irrigation, any additional pharmaceuticals or anesthesia applied, procedures performed, and placement of the buckle. Patient will receive a pill-count form at the end of the visit to keep track of rescue analgesic consumption. All patients

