## 14.0 Number of Subjects

*14.1 Indicate the total number of subjects to be enrolled and how this number was determined*

Sample Size Calculation as performed by [name] of VT and VTCSOM

$H_0$  = median post-operative pain equal in experimental and control groups

$H_A$  = median post-operative pain not equal in experimental and control groups

Median Pain Score Experimental: 1. SD = 1, IQR = 0-2

Median Pain Score Control: 3. SD = 2.5, IQR = .5 – 5.5

Alpha = .01, Power = 0.8

Effect Size,  $d$  = 1.05

Sample Size:  $n$  = 48

*14.2 If this is a multi-site study, indicate the number of subjects to be enrolled at this site and the total to be enrolled from all sites.*

n/a

14.3 *If applicable, indicate the number of potential subjects you expect to screen for enrollment, and the number of subjects you will need to complete the research procedures.*

n/a

14.4 *If the study has more than one procedure, indicate the total number of subjects to undergo each procedure separately.*

n/a

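### Section 5.2 names Student's t-test although 14.1 plans SDs of 1 and 2.5 and a coin flip sets the arm sizes; Welch's test corrects the standard error for one line of text

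*Combined protocol and SAP*

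**What the plan says.** Section 5.2 specifies "Parametric analysis of experimental and control groups using students' t-test for primary endpoint" and adds that "secondary endpoint of pain and analgesic consumption will be analyzed similarly". It does not say whether the variances are pooled, and no other section names an unequal-variance version.

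Section 14.1 plans for unequal spread: "Median Pain Score Experimental: 1. SD = 1, IQR = 0-2" against "Median Pain Score Control: 3. SD = 2.5", with "Alpha = .01, Power = 0.8" and a two-sided alternative. Section 8.1 has patients "randomized (by coin-flip) into one of two arms, the control or the experimental". Section 5.1 calls the trial a simple randomized one, and nothing fixes equal arm sizes.

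The primary endpoint in 4.1 is itself a significance statement, "Statistically significant reduction in pain as measured by 11-point Numerical Rating Scale at 1-day post-op", followed by "We are powered to detect a reduction in 2 points on the NRS scale". No confidence interval is planned.

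**The concern.** The pooled standard error is unbiased for the true one if the two SDs match or the two arms are the same size. The plan assumes unequal SDs and leaves the arm sizes to chance. When the arm with the larger SD (control) is the smaller one, pooling gives too much weight to the quieter arm and understates the uncertainty. When control is the larger arm, the reverse happens.

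These errors partly cancel over repeated coin flips, but the trial will report the single split that occurs. The primary conclusion is a significance test at a strict alpha of .01, so a standard error wrong by 10% or more bears directly on it, and on any interval reported beside it.

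**Working it through.** Splits are written control/triamcinolone. All tests are two-sided at alpha .01 unless stated.

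**Inputs.** SDs 2.5 (control) and 1 (triamcinolone), alpha .01, power 0.8, d = 1.05 and N = 48 from 14.1; a 2-point difference from 4.1; coin-flip allocation from 8.1. Dropout is not stated and is taken as zero.

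**1. The plan's own figure.** d = 2/√((1² + 2.5²)/2) = 2/1.904 = 1.05, as stated. An exact t-test calculation needs 23 per arm (46 in total) and has power 0.824 at 24 per arm. Inflating for a Mann-Whitney test by π/3 gives 24 per arm, which is 48. The stated N is therefore reproduced, within two patients on the t-test basis.

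**2. Arm sizes.** Control size ~ Binomial(48, 0.5).
- P(24/24) = 0.1146
- P(control smaller) = (1 − 0.1146)/2 = 0.443, and the same for control larger
- P(control ≤ 20) = 0.156, and the same for control ≥ 28

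**3. Standard errors.** With n_c control and n_t triamcinolone patients:
- pooled SE = √[s_p²(1/n_c + 1/n_t)], where s_p² = [(n_c − 1)·6.25 + (n_t − 1)·1]/46
- true SE = √(6.25/n_c + 1/n_t)

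At 20/28: s_p² = (118.75 + 27)/46 = 3.168; pooled SE = 0.521; true SE = 0.590; ratio 0.883 (11.7% too small).

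At 28/20: s_p² = (168.75 + 19)/46 = 4.082; pooled SE = 0.591; true SE = 0.523; ratio 1.132 (13.2% too large).

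At 24/24 the two agree exactly.

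**4. Simulation** (normal data with the plan's SDs; averages weighted by the binomial probabilities). Error is the rejection rate with equal means but SDs of 2.5 and 1. Power is for a 2-point difference.

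| Split | Student error | Welch error | Student 99% CI coverage | Student power | Welch power |
|---|---|---|---|---|---|
| 20/28 | 0.025 | 0.010 | 97.5% | 0.84 | 0.72 |
| 24/24 | 0.011 | 0.010 | 98.9% | 0.82 | 0.81 |
| 28/20 | 0.005 | 0.010 | 99.5% | 0.78 | 0.86 |
| Control smaller, average | 0.022 | 0.010 | 97.8% | 0.83 | 0.73 |
| Control larger, average | 0.006 | 0.010 | 99.4% | 0.78 | 0.85 |
| All splits, average | 0.014 | 0.010 | 98.6% | 0.81 | 0.79 |

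At 18/30 the SE ratio is 0.83 and Student's error is about 0.034. For a 95% interval, Student's coverage is 91.4% at 20/28 and 94.4% on average (Welch 95.0% on average). The mean 99% interval width is 3.03 NRS points for Welch and 2.96 for Student.

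**5. Sensitivity to the SD ratio.** Student's 99% interval coverage:

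| SD ratio | 1.25 | 1.5 | 2 | 2.5 |
|---|---|---|---|---|
| At 20/28 | 98.7% | 98.4% | 97.9% | 97.5% |
| Average over flips | 99.0% | 98.9% | 98.7% | 98.6% |

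With equal SDs (common SD 1.904), average power is 0.809 for Welch and 0.814 for Student.

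**6. Bounded scores.** The shape here is an assumption: beta-binomial integers from 0 to 10 with the plan's medians and SDs, and means 3 and 1. Coverage for Student against Welch is 97.2% vs 98.6% at 20/28, 98.6% vs 98.7% at 24/24, 99.4% vs 98.8% at 28/20, and 98.4% vs 98.7% on average. Welch is only approximate for a skewed score, but it depends far less on the split.

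**7. The planning SDs themselves.** Each equals half its stated IQR (2/2 = 1; 5/2 = 2.5), and no source is given. If those IQRs describe normal data, the SDs are 2/1.349 = 1.48 and 5/1.349 = 3.71, and average power falls to 0.39 (Welch) and 0.41 (Student). The ratio stays 2.5, so the relative SE error and the coverage figures are unchanged.

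**The case against.** The strongest reply is that the planned SDs belong to the planned effect, since they are attached to medians of 1 and 3. If triamcinolone does nothing, both arms should share one distribution, and Student's test then holds its level: 0.0102 against 0.0101 for Welch, averaged over coin flips, in simulated 0–10 scores. This stands. The error rates above apply to equal means with unequal SDs, a state that no section posits. What remains under the plan's own scenario is a wrong standard error, hence wrong coverage of any interval, and power that moves with the split for the wrong reason.

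Other points stand in part:
- **No interval is planned**, so the coverage figures matter only if one is reported.
- **The average effect is small.** Arms of 22 to 26 occur in 53% of trials (0.1146 + 2 × 0.1100 + 2 × 0.0973 = 0.529), where the SE error is at most about 6%.
- **The SD ratio is unsourced**, and at 1.25 the average effect vanishes. Welch then costs almost nothing.
- **Welch lowers average power to 0.79**, just below the planned 0.80, and to 0.72 at 20/28. Student's higher figure at 20/28 comes from an SE that is too small.
- **The name may have been meant loosely** and could include Welch. In that case one clarifying line settles the matter.
- **Section 14.1 states its hypotheses on medians**, and N = 48 matches a Mann-Whitney calculation. If 5.2 is later changed to a rank test, this edit falls away. That is a separate question, which Welch's test does not resolve.

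**Conclusion.** The concern holds, as a recommended improvement and not a fatal flaw. On the plan's own SDs the pooled standard error is wrong at every unequal split, and unequal splits occur in 88.5% of trials (100 − 11.5). The direction depends on chance. The size runs from about 3% at 23/25 or 25/23 to 12–13% at 20/28 or 28/20, with splits at least as uneven as these last two having probability 31% (2 × 15.6%).

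The conclusion assumes that Student's test means pooled variance, that the SD ratio is near the planned 2.5, and that no one drops out. The arithmetic is secure. How far this trial will be affected depends on the SDs it actually sees. Welch removes the bias in the standard error; on bounded, skewed scores its coverage stays slightly below nominal.

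**What to change.** In 5.2, replace Student's test for the primary endpoint with Welch's unequal-variance t-test, two-sided at the .01 level of 14.1, and report the difference in means with its 99% confidence interval. Use the same test for the pain and analgesic outcomes that follow the primary method, for consistency only: the documents give no SDs for them, so no gain is claimed there.

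The cost is one line of text and no extra patients. There is no average power gain: about 2 points are given up under the planned SDs and about 0.5 points if the SDs are equal. Naming the test in advance also rules out choosing between the two versions after the split is known.

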## **7.0 Study Intervention(s)/Investigational Agent(s)**

*7.1 Describe the study interventions (including behavioral interventions) and/or investigational agents (e.g., drugs or devices) to be used in this study.*

- *Drug/Device Handling:*  
Triamcinolone will be stored in the operating facility according to package instructions: at controlled room temperature, 20° to 25°C (68° to 77°F). Vial will be stored in carton to protect from light, and will be stored upright. In the operating room, the vial will be opened according to sterile procedure by a nurse and prepared for injection by the surgeon.

## Using Triamcinolone Acetonide to Reduce Pain after Scleral Buckle Surgery

7.2 *List the name of all drugs (including any vitamins, supplements, herbs, or nicotine) to be used in the study. Indicate whether they have FDA approval, and list any limitations for their use.*

Triamcinolone Acetonide injectable suspension. FDA Approved.

Marcaine (Bupivacaine Hydrochloride .75%). FDA Approved.

7.3 *List all devices, how they will be used, their purpose in the study, and if they will be used in a manner consistent with their approved uses. If they will be used in ways that are not yet FDA approved, indicate whether they need an IDE or a determination that they are exempt from the IDE Determination. If a determination of significant risk or non-significant risk is needed for any of the devices, include the researcher's recommendation for each of those devices.*

N/A

7.4 *If the drug is investigational (has an IND) or the device has an IDE or a claim of abbreviated IDE (non-significant risk device), include the following information:*

N/A

## 8.0 Procedures Involved

8.1 *Describe and explain the study design.*

Randomized Control Trial. Subjects will be patients at Vistar Eye Center who are undergoing scleral buckle surgery for rhegmatogenous retinal detachment. Patients of this indication will be consented and enrolled in the trial as detailed in section 24, and randomized (by coin-flip) into one of two arms, the control or the experimental. Patients in both arms of the study will be screened for IOP via handheld digital tonometry (tonopen) and will undergo standard scleral buckle procedures, including irrigation with 1 ml .75% Marcaine for local anesthesia (as is standard for all surgeries). At time of surgery, patients in the experimental group will receive irrigation of 1 ml (40 mg/mL) triamcinolone around the bed of applied scleral buckle distributed equally in all 4 quadrants (.25 ml per quadrant) under the tenon layer of the eye. Patients in the control group will be given irrigation around the applied scleral buckle of 1 ml balanced salt solution instead of triamcinolone. Patients will be masked to the treatment group assignment. The surgeon cannot be masked, as the triamcinolone solution is white and the balanced salt solution is clear. Intraoperative details will be recorded in the EMR about the surgery in both groups, including duration of surgery, time of irrigation, any additional pharmaceuticals or anesthesia applied, procedures performed, and placement of the buckle. Patient will receive a pill-count form at the end of the visit to keep track of rescue analgesic consumption. All patients

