### 3.2 *Describe any relevant preliminary data*

The use of Triamcinolone Acetonide sub-tenon irrigation has been done as standard at Vistar for scleral buckle surgeries for the last 2 years by [name] and [name]. Observations by the two surgeons suggest that there is a great analgesic effect for patients 24 hours post-surgically when compared to patients not given TA. There have been no noted adverse effects resulting from this use.

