## Using Triamcinolone Acetonide to Reduce Pain after Scleral Buckle Surgery

will be given appointments for post-operative day 1, and 1-2 weeks post-operative as is standard practice.

On post-operative day one, primary outcome data will be obtained by a blinded examiner who will be giving the patient a form which asks about the patient's pain score by reference to an 11-point numbered rating scale (0-10). On the same form, patients will also be asked about post-operative nausea and vomiting for secondary endpoint, which will be scored from 0-6 by adding the points for question II and question III from the pain and nausea survey. The form will be collected by the same examiner when completed. Pill count sheet will be collected and additional sheet will be given for patient to track analgesic use between first and second visit.

Patient will then have regularly scheduled visit with the surgeon who will be screening the patient for success of surgery, adverse events, and will examine pain and nausea scores to ensure both are well controlled. The physician will be ensuring the patient's safety, and will be allowed to prescribe any medications deemed medically necessary for control of side effects, nausea, and pain. IOP of all patients will also be measured at this visit.

At second post-operative visit (1-2 weeks), patients' IOP will be measured again for safety endpoint. Patient pill count sheet will be collected.

Patients will be filling out 11-point NRS pain score and post-operative nausea and vomiting sheet again during office visit and it will be collected by blinded examiner. Patient will then be examined by surgeon again for success of surgery, adverse events, and control of pain and nausea.

	Before Surgery	Day of Surgery	Between Surgery and First Follow-Up Visit	First Follow-Up Visit (1 day after surgery)	Between 1 st and 2 nd Follow-Up Visits	Second Follow-Up Visit (1-2 weeks after surgery)	Long-Term Follow-Up (6 months )
Location	Clinic	Surgery Center	Home	Clinic	Home	Clinic	Phone
Procedures	The doctor will explain the study to patient	Everyone: Scleral Buckle Surgery. Experimental Group: Triamcinolone (steroid) will be applied during surgery. Control Group: Saline solution will		Everyone : will be examined by the doctor for safety		Everyone : will be examined by the doctor for safety	

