## 12.0 Inclusion and Exclusion Criteria

### 12.1 Describe how you will screen individuals for eligibility. When will screening occur and what procedures will you use? Upload any screening scripts or surveys to Protocol Management.

Individuals will be screened at time of diagnosis. All patients who are determined to need scleral buckle surgery for rhegmatogenous retinal detachment will be screened for eligibility. Screening for the trial will be done by the surgeon, who will be reviewing the medical history at time of visit via EMR. If patient does not fail the exclusion criteria, the patient will be consented for enrollment in the trial. There are no screening scripts or surveys that will be used.

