## Using Triamcinolone Acetonide to Reduce Pain after Scleral Buckle Surgery

The patient will be consented in the clinic patient exam room, immediately following consultation with the doctor about the planned surgical procedure. The consultation will be done by the doctor who is well trained on the procedures and risks. The doctor will also be able to answer any more specific questions that the patient may have.

- *The time interval between sharing the consent information with the prospective subject and obtaining consent. For lab, interview, and focus group studies, the Virginia Tech IRB prefers that subjects have at least 24 hours to review the consent form and study information before the appointment where consent will be obtained. For simple online survey studies, you can typically present the consent information immediately before subjects begin participation.*

The obtaining of consent will occur directly after the sharing of consent information. However, the patient will be given a copy of the consent forms and the surgery will not usually take place until the next day or longer still, giving the patient sufficient time to review the materials and change their decision to withdraw or provide consent by notifying any staff member up until the moment right before surgery.

- *If applicable, processes to ensure ongoing consent or assent (e.g., for multiple sessions; for research in which a minor will turn 18 during the study; for longitudinal research with minors who will later be asked to provide or affirm their assent).*

As there is no more than minimal risk to the patient after the original intervention, we do not believe this is necessary.

- *Please review “SOP: Informed Consent Process for Research (HRP-090)” for recommended procedure. Describe your process, being sure to include:*
  - *The name and role of all study personnel who will be trained and certified by the PI to conduct the consent process*
    - [name] M.D. (PI)
    - [name] Jr. M.D.
    - [name], Medical Student, Research Coordinator
  - *The time that will be devoted to the consent discussion*  

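### Allocation is by coin flip with no concealment, independent holder or record described, so a repeated or overridden flip would leave no trace

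*Combined protocol and SAP*

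**What the plan says.** Section 5.1 calls the trial a "Simple randomized controlled trial comparing two groups in reducing post-operative pain from scleral buckle surgery". Section 8.1 gives the method in one phrase: after consent and enrolment, patients are "randomized (by coin-flip) into one of two arms, the control or the experimental". The text available for review does not say who flips, when, who witnesses it, where the result is written down, or how it is withheld. It mentions no list, envelope, central service or blocking. Section 6.0 (Setting) is not in that text, but 8.1 is where the method is stated.

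Other sections bear on this:

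- **Roles.** Section 12.1: "Screening for the trial will be done by the surgeon". Section 15.1 has the surgeon or the research coordinator recruit.
- **Masking.** Section 8.1: "The surgeon cannot be masked, as the triamcinolone solution is white and the balanced salt solution is clear". The same section says "Patients will be masked to the treatment group assignment", and that on day one "primary outcome data will be obtained by a blinded examiner".
- **Prior belief.** Section 3.2: "Observations by the two surgeons suggest that there is a great analgesic effect for patients 24 hours post-surgically". Section 3.3 says that several surgeons at the centre already use triamcinolone in all their scleral buckle operations.
- **Timing.** Section 24.1: "the surgery will not usually take place until the next day or longer still". Patients may change their decision until just before the operation.
- **Withdrawal.** Under section 16.3, a patient who withdraws consent, before or after surgery, has no data extracted. Survey forms already completed are destroyed.

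**The concern.** Randomisation protects the comparison only if nobody with a stake in the assignment can change it, or act on it, before the patient is committed. Here the people nearest the assignment screen, may recruit, and deliver the treatment knowing what it is. Some of them already believe in one arm. A coin flip with no witness or log can be done again or set aside, and nobody could show afterwards that it was not.

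If the flip is made in the gap between consent and surgery, a known result can also affect who goes ahead. Section 16.3 would then remove that patient from the dataset. Selection of this kind shifts the baseline of the two arms, and no choice of test or adjustment reliably repairs it. With 48 patients, a few such cases could matter, and a reader of the final report would have no means of ruling them out.

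**Working it through.** **1. Which safeguard covers which step**

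| Step | What the plan provides | Protected? |
|---|---|---|
| Next assignment unpredictable at enrolment | Fair coin, flipped after enrolment (8.1) | Yes, if done as written |
| Result cannot be repeated or overridden | Nothing described | No |
| Result withheld until treatment is due | Nothing described; surgery usually a day or more after consent (24.1) | Not stated |
| Loss after assignment is visible | Withdrawn patients have no data extracted (16.3) | No |
| Pain reported and collected without knowledge of arm | Patient masked, examiner blinded (8.1) | Yes |

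The masking acts at the last step. The gap lies in the three steps before it.

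**2. The plan's sample size (14.1)**

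Inputs: medians 1 and 3, SDs 1 and 2.5, alpha .01 (two-sided, since the alternative is inequality), power 0.8.

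- d = 2 / √[(1² + 2.5²)/2] = 2 / 1.904 = 1.05, as stated.
- A t-test needs 23 per arm, or 46. Allowing for the rank test's efficiency of 3/π gives 24 per arm, or 48, as stated.

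The figure is reproduced on the basis of equal arms. The documents do not themselves state 24/24.

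**3. How uneven a coin flip leaves the arms**

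The number in one arm is Binomial(48, 0.5). The probability that the smaller arm has k or fewer patients (k < 24) is 2 × Σ C(48, i)/2⁴⁸, for i = 0 to k.

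- 19/29 or worse: 2 × 0.0967 = 0.193
- 18/30 or worse: 0.111
- 17/31 or worse: 0.059
- Expected absolute difference between arms: 5.5 patients

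**4. What unevenness costs in power**

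Noncentral t, 46 degrees of freedom, two-sided .01, d = 1.05, noncentrality = d√[n₁n₂/(n₁+n₂)].

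- 24/24: 1.05 × √12 = 3.64, power 0.824
- 19/29: 1.05 × √(551/48) = 3.56, power 0.803
- 18/30: 1.05 × √(540/48) = 3.52, power 0.793
- Averaged over all coin-flip splits: 0.814

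The average loss is 0.824 − 0.814 = 0.010, about 1 percentage point.

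**5. What blocking would cost**

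An unmasked surgeon who knew that blocks had fixed size 4 could guess (1/2 + 2/3 + 2/3 + 1)/4 = 71% of assignments, against 50% for a fair coin. For fixed blocks of 6 the figure is 68%. Random, undisclosed sizes of 4 or 6 reduce this predictability and, in an unstratified list, bound the arm difference at 3.

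**The case against.** **A fair coin is the least predictable method there is.** This stands. A reader might infer that assignments can be foreseen. The documents do not support that: enrolment comes before the flip, and the next result cannot be known. The weakness is that a result, once seen, can be changed or acted on.

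**Silence is not proof of an open procedure.** This also stands. The plan does not say that allocation is unconcealed. The flip might be made in the operating room and written down. The record keeps whether triamcinolone was applied (9.1) and the time of irrigation (8.1), but that is treatment given, not treatment assigned, and it would look the same after a repeated flip.

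**The roles are not all one person's.** Section 3.2 reports the view of two surgeons, section 26.1 says four operate, and a coordinator may recruit. This narrows the exposure without closing it.

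**Simple randomisation is a legitimate choice, and imbalance costs little.** Agreed, which is why blocking is only optional here.

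Two stronger readings are tempting. The first is that uneven arms inflate the type I error. With SDs of 2.5 and 1 and equal means, Student's t at nominal .01 does reject about 0.029 of the time at 19 control/29 triamcinolone. But those SDs describe the alternative. If triamcinolone does nothing, the arms share one SD, and the simulated error is 0.010 at 24/24, 19/29 and 17/31. Even under unequal SDs the average over coin-flip splits is 0.014, against 0.011 at 24/24, and Welch's test holds about 0.010. That is a question of which test to use. The second is to put a figure on steering by supposing some number of swapped patients. Nothing in the documents supports such a number, and even the direction is open: a surgeon who trusts the drug might steer patients expected to have more pain towards it.

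**Conclusion.** The concern holds for concealment and traceability. As described, the procedure has nothing to stop or reveal a repeated or overridden flip, or a withdrawal influenced by a known assignment. The incentive is documented, and the masking does not reach this step. The conclusion assumes that no safeguard is set out in text not available for review. It does not assume that anyone has misused or would misuse the procedure.

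The size of any selection bias is unknown and cannot be derived from the documents. Imbalance between arms is likely (19% for 19/29 or worse) but is a minor issue, at about 1 point of average power. The documents do not support a claim that assignments are predictable, or that the coin flip by itself breaks the .01 error rate.

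This should be settled before further patients are randomised, because concealment and a log cannot be added afterwards.

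**What to change.** Rewrite the allocation sentence in section 8.1 so that it states the following:

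- The assignment comes from a computer-generated list prepared by someone who neither recruits nor operates.
- Assignments are held in sequentially numbered, sealed, opaque envelopes.
- Each envelope is opened in the operating room only when the irrigation is due.
- The envelope number and time of opening are logged for every patient. The entry is kept if the patient later withdraws, so that numbers assigned and lost can be reported by arm. Section 16.3 should be worded to allow this.

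Optionally, build the list in permuted blocks of randomly varying, undisclosed size. This keeps the arms close to 24/24, at the price of some predictability for an unmasked surgeon. The power gain alone does not require it.

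The cost is protocol wording and about an afternoon to prepare the list and envelopes. The sample size, visits, treatments and timing of consent stay as they are.

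### Section 8.1 does not say when the unmasked surgeon learns the arm, so additional drugs given at surgery may be chosen with that knowledge and could shift day-1 pain in either direction.

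*Combined protocol and SAP*

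**What the plan says.** Section 8.1 has patients consented and then "randomized (by coin-flip) into one of two arms, the control or the experimental". The coin-flip comes before surgery in that account. The section does not say who flips the coin, who sees the result, or when the surgeon is told.

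On masking, 8.1 says "Patients will be masked to the treatment group assignment" and, on post-operative day 1, "primary outcome data will be obtained by a blinded examiner". For the operator it says "The surgeon cannot be masked, as the triamcinolone solution is white and the balanced salt solution is clear". Section 7.1 adds that "the vial will be opened according to sterile procedure by a nurse and prepared for injection by the surgeon".

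Both arms receive standard scleral buckle procedures, with the same 1 ml Marcaine irrigation, and 1 ml of either triamcinolone or balanced salt solution around the applied buckle. Beyond these, the intra-operative details to be entered in the EMR for both groups include "any additional pharmaceuticals or anesthesia applied, procedures performed, and placement of the buckle". This is a recording rule: it neither permits nor limits anything. Section 7.2, which asks for all drugs used in the study, names only triamcinolone and Marcaine.

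Section 3.2 gives the surgeons' prior view: "Observations by the two surgeons suggest that there is a great analgesic effect for patients 24 hours post-surgically". Section 3.3 says that several surgeons at the centre already use triamcinolone in all these operations.

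Section 5.2 analyses the primary endpoint with a Student's t-test and mentions no covariate or sensitivity analysis. The day-1 pill count is a secondary endpoint (section 4.1). The revision history says that revision 1 added a pain protocol, but no such protocol appears in the supplied text.

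**The concern.** The primary endpoint is pain about 24 hours after surgery. Additional local anaesthetic, anti-inflammatory or analgesic drugs given at the operation, or supplied at discharge, can act on pain within that window. If the surgeon knows the arm when choosing them, the choice can differ by arm.

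The documents also give a reason why it might. For a surgeon who already uses triamcinolone routinely, a saline assignment withholds the usual treatment, and adding something else is an understandable response. That would shrink a real difference. Lighter co-treatment of controls, or extra co-treatment in the triamcinolone arm, would do the reverse and could produce a difference where none exists.

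The masking that the plan does provide protects how pain is reported and collected. It does not protect what was given in the operating room. An unadjusted two-group test would attribute the whole difference to triamcinolone.

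**Working it through.** **Inputs from the documents.** Section 14.1: SD 1 (experimental) and 2.5 (control), medians 1 and 3, alpha 0.01, power 0.8, d = 1.05, n = 48, and a two-sided alternative. Section 4.1: target difference of 2 points. I assume 24 per arm; a coin-flip does not guarantee it.

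**Reproducing the plan's figures.**
- Pooled SD = sqrt((1² + 2.5²)/2) = sqrt(3.625) = 1.904.
- d = 2/1.904 = 1.05, as stated.
- The noncentral-t calculation at two-sided alpha 0.01 and power 0.8 gives 22.9, so 23 per arm (46 in total). Dividing by the Wilcoxon efficiency 3/π gives 24 per arm, which is 48 and fits hypotheses stated on medians.
- With 24 per arm, SE = 1.904 × sqrt(2/24) = 0.550. Noncentrality for 2 points is 2/0.550 = 3.64, and the power of the t-test on 46 df is 0.824.

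**Inputs not in the documents (assumed).** An additional co-treatment lowers day-1 pain by 1.5 points, and its use differs between arms by 20 or 30 percentage points. The net shift is b = effect × difference in use: 1.5 × 0.20 = 0.30, and 1.5 × 0.30 = 0.45.

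**Extra co-treatment in controls, true effect 2 points.**

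| Net shift b | Observed difference | Power |
|---|---|---|
| 0 | 2.00 | 0.824 |
| 0.30 | 1.70 | 0.657 |
| 0.45 | 1.55 | 0.557 |

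**Shift in favour of triamcinolone, no true effect, b = 0.45.**
- With the SDs of 14.1 (SE 0.550), the rejection rate is 0.037 against a nominal 0.01.
- With no true effect, unequal SDs are hard to justify. With SD 2.5 in both arms, SE = 2.5 × sqrt(2/24) = 0.722 and the rejection rate is 0.025.

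**Range.** Letting the assumed effect run from 1 to 2 points and the imbalance from 20% to 30%, b runs from 1 × 0.20 = 0.20 to 2 × 0.30 = 0.60, and power from 0.72 to 0.45. A small imbalance does little harm: 5 percentage points in a 1-point co-treatment gives b = 0.05 and power 0.80.

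**Which choices are exposed.** The surgeon prepares the study solution and can see its colour, so knows the arm by then at the latest. Drugs chosen after that point are exposed under any reading. Drugs chosen earlier are exposed only if the coin-flip result reaches the surgeon earlier, which 8.1 neither says nor rules out. Free prescribing at the day-1 visit follows the completed pain form and cannot bias the primary endpoint.

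**The case against.** The strongest reply has four parts.

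*Timing.* A reader might infer that the surgeon knows the arm before choosing any anaesthesia. The documents do not say so. The only reason given for not masking the surgeon is the colour of the solution, and that solution is irrigated around a buckle already in place. If the arm is learned only then, earlier anaesthesia cannot be affected, and what remains is end-of-surgery and discharge drugs. This stands, so the point is limited to what the surgeon may know.

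*Permission.* A reader might also take the EMR sentence as allowing unlimited extra drugs. It only requires recording, and the Marcaine is fixed equally in both arms. This stands too. What remains is that the supplied text sets no common approach to additional drugs.

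*Post-operative analgesia.* The pain protocol in the revision history may fix it for both arms and may sit in a removed page or an attachment, so its absence here cannot be held against the plan. Home use is also visible through the day-1 pill count, compared by arm and recorded by masked patients. This weakens the discharge part of the concern, which in any case assumes that the operating team orders those drugs. The pill count does not show what was given in the operating room.

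*Magnitude.* The effect and the imbalance are assumed, and a small imbalance costs almost nothing. This is correct, and the figures are offered only as an illustration.

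**Conclusion.** The concern holds in a limited form. The surgeon is unmasked and has a stated expectation of benefit. The time of disclosure is not given, additional intra-operative drugs are recorded but not standardised in the supplied text, and the primary analysis does not use the record. Unequal co-treatment is therefore possible, and day-1 pain could be biased in either direction.

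The documents do not show that such bias will occur, and they do not give its size. The figures rest on 24 per arm, the SDs of 14.1, an assumed 1.5-point co-treatment effect and an assumed 20-30 percentage point imbalance. On those terms power falls from 0.82 to 0.66-0.56, or the false-positive rate rises from 1% to about 2.5-3.7%. If the pain protocol standardises post-operative analgesia in both arms, the exposure narrows to drugs given during the operation. The change is worth making because it is cheap, and because analysis cannot reliably undo treatment chosen with knowledge of the arm.

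**What to change.** In section 8.1, state that the assignment is concealed from the surgeon until the moment of study irrigation. By then the Marcaine and any planned additional anaesthetic have been given and the usual post-operative orders have been entered. The surgeon still prepares the study solution as in 7.1, but only after the reveal.

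Leave anything added later to clinical judgement, and log it with drug, time and reason. In section 5.2, commit to tabulating all recorded co-treatments and the day-1 pill count by arm beside the primary result. If the pain protocol applies to both arms, cite it in 8.1.

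The cost is one reordered step, about a minute per case, and a short log. No drug, dose or clinical rule is proposed.
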